Efficacy of intraoperative CT feedback of wedge resected lung for the assessment of surgical margin

Protocol Version #2

Date: 26APR2024

Research Objectives

Aim1: To assess how surgical outcomes are impacted by intraoperative CT feedback.

Aim2: To assess the validity of the additional resections.

Study Background

Lung cancer is the most prevalent cancer and the leading cause of cancer death in Canada. In 2020, lung cancer resulted in the deaths of 21,200 Canadians (1). The high mortality reflects both its high incidence and low survival. Although it is one of the most aggressive malignant tumors, as with many other types of cancer, patients can live cancer-free if the diagnosis is accurate and timely treatment is administered. Low-dose computed tomography (LDCT) scans can help find abnormal areas in the lungs that may be cancerous. Research has shown that scanning patients at higher risk of lung cancer using LDCT saved more lives compared to chest x-rays (2). In Canada, opportunistic screening is occurring in at least six provinces and implementation of organized programs is expected in the coming years (3). The increased prevalence of CT screening and advances in diagnostic technology, particularly the widespread use of thin-slice computed tomography, have enabled increased detection of early-stage small lung cancers (4). Early-stage lung cancer is often featured as a ground-glass opacity (GGO) associated with a pathological lepidic growth pattern that is considered to be related to a more favorable prognosis (5). Therefore, these GGO-dominant lung cancers could be optimal candidates for sublobar resections, which is to remove a section of a lobe of the lung that contains the lung cancer and a margin of healthy tissue around the cancer. This is an alternative to the conventional, more radical, pulmonary lobectomy (6, 7). Sublobar resection, including segmentectomy and wedge resection, is less invasive, sparing more healthy lung tissue and is associated with improved patient recovery. However, an increasing number of hazy lung tumors are also being detected, which are difficult to localize intra-operatively as they are

neither palpable, nor visible to the naked eye. To address the challenge of identifying small pulmonary nodules during surgery we have studied the accuracy of CT-guided insertion of microcoils prior to lung surgery (8). In addition, CT-guided microcoil localization was also associated with excellent recurrence-free survival for small lung tumors (9). The other challenge regarding sublobar resection is the possibility of locoregional cancer recurrence due to positive stump cytology and insufficient surgical margins which is defined as the amount of normal lung tissue excised around the tumor. These factors correlate with postoperative local recurrence but sometimes contradicted the results, in other words, positive stump cytology with negative surgical margin and vice versa (10). Therefore, keeping sufficient safety margins is important to ensure a complete resection. Currently, at least 15 mm distance or tumor size distance from the gross tumor is considered as a safe surgical margin in sublobar resections for prevention of local surgical recurrences in lung cancer (10, 11). Same can be said for metastatic lung tumors where margin length has been reported to be associated with the predicted probability of local recurrence (12, 13).

If the surgical margin is insufficient, additional resection or postoperative radiation therapy may be required which can cause patients additional stress. To date, there is no established method for confirming whether sufficient surgical margin was obtained during surgery, only as a pathological specimen post operation. To address this intraoperative limitation of margin assessment, we evaluated a radiological evaluation for sublobar resection specimen using CT during surgery. This method was demonstrated to be feasible for the assessment of the surgical margin as described below. However, the previous study did not include any feedback of the results intraoperatively, which did not contribute to decision-making and treatment strategy. The ability to accurately evaluate surgical margins intraoperatively could reduce the risk of locoregional recurrence and eliminate the need for additional treatment after surgery. Moreover, optimal intraoperative feedback to surgeon could influence surgical decision making and contribute to the satisfactory outcome.

Pre-clinical study

- 1) Protocol establishment for lung specimen preparation
Pre-clinical ex-vivo pig lung experiments assessed the feasibility of the image

acquisition and surgical margin measurement procedure by CT. A total 30 pig lung resected specimen were evaluated for the assessment. Resected lungs required re-inflation by injecting air to obtain the specimen CT image with sufficient quality for further analysis. After image acquisition, the lung specimen was instilled with 10% formalin neutral buffer solution using a 25-gauge needle and then soaked in the solution for at least 24 h. Microscopic histological specimen analysis was possible after standard tissue processing including fixation, gross assessment, and staining. We concluded that the additional steps can be easily integrated into the existing work flow without compromising specimen integrity since all imaged specimens were adequate for subsequent histopathologic analysis.

2) Evaluation of CT margin measurement

In order to simulate the surgical margin measurement by CT after sublobar lung resection, a pseudo lung nodule was created by injecting agar gel into the pig lung specimen. We confirmed that it was possible to measure the distance between the edge of pseudo tumor and cut surface. This CT based margin assessment measurement was then compared to the measurement carried out by pathology, which is the gold standard for assessing margin length. In all evaluated lungs (n=30), surgical margin measured by CT was 3.50 mm +/- 2.69 mm greater than that measured by pathology. This discrepancy was possibly attributable to tissue shrinkage by formalin fixation during standard pathology process (14). Based on the result of this preclinical study, clinicians should keep in mind that margin length shortening would be expected by tissue processing.

Clinical study

1) Protocol

The Previous clinical study was conducted to assess the feasibility of CT margin measurement (REB #22-5528). From October 2022 to March 2023, patients treated with sublobar resection (Segmentectomy or wedge resection) for clinical lung malignancies were introduced to the study by their treating surgeon. Of those, the patients who provided consent to the study after explanation by research coordinator were enrolled. Patients data including age, gender, CT findings (tumor diameter, location, distance between pleura to tumor), surgical data (surgical procedure, preoperative marking, operative time, blood loss), pathological diagnosis, margin data (CT margin, pathological margin) were collected.

CT margin was calculated as follows: i) resected lung specimen was inflated with 25-gauge needle and an appropriately syringe, while monitoring to prevent alveolar wall destruction using a pressure transducer. ii) The specimen was placed on a CT scanner with adjustment of staple line perpendicular to CT axial line and scanned CT in Spatio-temporal targeting and amplification of radiation response (STTAAR) innovation center. iii) CT margin was defined as the distance between tumor and tumor side of the staple line, and measured. After the assessment, the specimen was delivered to the surgical pathology department, and standard pathological examination was performed.

2) Results

54 patients were enrolled. In this study. In 4 patients (7.4%), poorly inflated specimen caused the tumor to be undetectable, which we subsequently excluded. Consequently, 92.6% of cases, 50 patients (52 specimens) were analyzed. Surgical margin measured by CT was significantly longer than pathological margin (11.74 ± 8.52 VS 10.08 ± 7.22 , $p = 0.033$). 21% surgical margin length reduction was observed from CT to pathological assessment. Medial correlation was found between CT assessed margin and pathological margin ($r = 0.7679$). Margin assessment for resected lung is feasible and accessible way to identify tumor and surgical margin during surgery. Surgeons should be aware that CT assessed surgical margin will be longer than pathological margin.

Sample size

We aim to evaluate 80 cases over 2 years. We would like to include all 9 thoracic surgeons in our division to evaluate the impact to the surgical outcome “surgical margin” over the course of the study. As this is unlikely as not all surgeons will perform wedge resections, we will enroll consecutive patients regardless of who the attending surgeon is.

Patient Groups

Inclusion criteria:

- Patients scheduled for lung wedge resection for primary lung cancer or metastatic lung tumor (included suspected lesions).

- 18 years of age or older.

Exclusion criteria:

- Any patients with inability to give informed consent
- Wedge resection for non-therapeutic purpose, e.g. diagnostic purpose.

Study Plan and Methods

This is a single center clinical trial. We will ask thoracic surgeons in our institution to work together for this research. A total of 80 patients scheduled for wedge resections for lung malignancies (including suspected patients) will be enrolled in this study. The attending surgeon will introduce the study to the patients and a research coordinator will then go through the consenting process, answer any questions and enroll the patient if they wish to participate within one month before surgery.

We will enroll 80 patients in 2 years for this study. Prior to first surgery, every surgeon will be asked to complete a questionnaire 1 to investigate the background of surgeon. At each surgery, we ask for questionnaire 2 orally before and after resection to assess the contribution of feedback to margin results. Once the wedge resection is performed, the resected specimen will be brought to 7th floor in STTARR innovation center in Princess Margaret Cancer Research Tower (PMCRT). Resected lung specimen will be inflated with 25-gauge needle and appropriately sized syringe. The air injection pressure as well as the total inflation pressure will be continuously monitored to prevent alveolar wall destruction using a pressure transducer. For the precise surgical margin measurement, the staple line is adjusted perpendicular to CT axial line. Surgical margin will be measured and its image will be captured. Surgical margin is defined as the distance from tumor to the tumor side of staple line (not including the width of staple line). The data (included CT image and CT surgical margin) will be numbered and exclude individual information (only include study number and date). The data will be transferred from CT scan to our laptop using universal serial bus (USB), then shared with surgeons by tablet in operating room through online storage service

such as OneDrive or directly with laptop or USB. These processes are expected to take about up to 20 minutes. Surgeons will wait and refer to these results, and make a decision if additional resection should be made. The lung specimen will be delivered to the pathological laboratory and routine pathologic work up will be proceeded per standard care, including fixation, gross assessment, and selection of clinically relevant tissue blocks for sectioning, staining, and microscopic assessment. Within several days after surgery, we will send the CT measured margin length and reconstructed 3D image of the resected specimen to the attending surgeon, and ask them to complete the rest of questionnaire 2. This is to evaluate the usefulness of the CT image feedback and the surgeon's satisfaction for each case.

Additionally, once the pathological result for each patient is revealed, surgeons will receive the results of the margin length comparison (CT based margin and pathological margin). After the total course of surgery, we will ask each surgeon individually for questionnaire 3 after feedback of the individual result of this study to assess the satisfaction by intraoperative feedback.

Benefits

Intraoperative feedback of surgical margin measured by CT correlates to pathological margin length, and could help make a decision for additional resection. Patients with a confirmed sufficient margin could have better local cancer control.

Risks

Additional resection could induce complication such as air leakage.

Extra time commitment for patients

The entire intraoperative feedback process takes about up to 20 minutes, further increasing the operation time.

Outcome Measures

The primary outcome of the study will include (1) the contribution of intraoperative feedback to treatment decision, and its validity, and (2) assessing how intraoperative feedback affects surgical margins over the course. The secondary outcome will be the assessment of surgeons' satisfaction with intraoperative

feedback.

Statistics

A linear mixed model will be performed to analyze the difference of the process between expected and actual margin over the course. Pearson's correlation analysis will be performed to analyze the correlation between the parameters measured on CT and on pathological analysis. Limits of agreement analysis will be performed per the Bland-Altman method to evaluate agreement between preoperative expectation for surgical margin and actual margin. ROC curves will be used to assess the CT margin to predict short pathological margin. GraphPad Prism8 (GraphPad Software, La Jolla, CA, USA) and R (for linear mixed model) will be used for statistical analysis. All p-values will be based on a two-sided hypothesis, with p-values < 0.05 indicating statistical significance.

Data Collection and Monitoring

The following data will be collected prospectively using source documents and a database specially constructed for the purpose. Data will be collected prospectively on all patients. Due to the low risk and influence for the patients involved in this study, a DSMB is not required.

- (1) Patients' background (age, gender, body weight, body mass index, history, smoking habit, preoperative diagnosis)
- (2) Preoperative CT information (tumor location, tumor size, CT appearance, Consolidation tumor ratio, distance between tumor and pleura)
- (3) Surgical information (surgery date, attending surgeon's study number, operative procedure, operative duration, preoperative marking, intraoperative CT image acquisition time, tumor size in intraoperative CT, margin length in intraoperative CT, additional resection, procedure change, intraoperative findings)
- (4) Pathological results (pathological diagnosis, tumor size, tumor spread through air space, pathological margin length)
- (5) Others (postoperative complication, length of stay)
- (6) Questionnaire results including surgeons' study number (see questionnaire section)

Access to Source Data/Documents

Access to the study data will be permitted for study investigators, coordinators,

and UHN REB.

Consent

All patients will receive both verbal and written information about the study and will be asked to give informed consent using study-specific consent forms. Nine thoracic surgeons in the division of thoracic surgery in Toronto General Hospital has received the explanation of this study and accepted to participate in this study in the previous conference. We will ask them to provide written consent for this study prior to the study.

Data Handling and Record Keeping

All data will be de-identified. Each subject will be given a study number with data stored securely in a locked cabinet. As described in the consent form, we will maintain a list for each patient, study number for the specimen, corresponding CT scan identification and questionnaire. This list will be kept by the study investigator in a secure place, separate from the study file for up to 10 years. We will follow storage, transport and destruction of confidential information policy.

References

3. [Internet] CPAC. Lung cancer screening in Canada environmental scan 2019-2020. at: <https://s22457pcdnco/wp-content/uploads/2021/01/lung-cancer-screening-environmental-scan-2019-2020-Jan132021-ENpdf>.
6. Ginsberg RJ, Rubinstein LV. Randomized trial of lobectomy versus limited resection for T1 N0 non-small cell lung cancer. Lung Cancer Study Group.

Ann Thorac Surg. 1995;60(3):615-22.

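### Does enrolling 80 patients fall short of the aim to evaluate 80 cases, given that 7.4% of CT scans failed in the earlier study?

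*Protocol*

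**What the plan says.** The Sample size section of the protocol gives its target as "We aim to evaluate 80 cases over 2 years". It then mentions the surgical margin as the outcome of interest and ends by saying that consecutive patients will be enrolled whoever the surgeon is. Study Plan and Methods gives the same number twice as an enrolment figure: "A total of 80 patients scheduled for wedge resections for lung malignancies (including suspected patients) will be enrolled in this study", and "We will enroll 80 patients in 2 years for this study". No effect size, standard deviation, power or precision target is attached to the 80, and there is no over-enrolment or replacement rule.

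The failure rate comes from the earlier feasibility study, described under Clinical study. Its Results state: "In 4 patients (7.4%), poorly inflated specimen caused the tumor to be undetectable, which we subsequently excluded". They continue: "Consequently, 92.6% of cases, 50 patients (52 specimens) were analyzed". That study enrolled "patients treated with sublobar resection (Segmentectomy or wedge resection) for clinical lung malignancies", so it was not confined to wedge resections. The preparation of the specimen is carried over: "Resected lung specimen will be inflated with 25-gauge needle and appropriately sized syringe".

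The Statistics section lists a linear mixed model and a Bland-Altman analysis of expected against actual margin, Pearson's correlation between CT and pathology, and this: "ROC curves will be used to assess the CT margin to predict short pathological margin". No number of patients is given for any of these analyses.

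**The concern.** The evaluation target equals the enrolment target, so read literally the two agree only if every scan succeeds. The protocol's own data, reported just above the Sample size section, make that unlikely. The CT margin is also what the surgeon waits for and acts on, so a failed scan leaves no figure to feed back. If the 80 were a count of usable CT margins, the trial would be expected to end about six short, and a reader would overrate the size behind the CT-based analyses. Had the 80 come from a power or precision calculation, that shortfall would erode a stated property of the design.

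**Working it through.** **Inputs.** Enrolment is 80 (Sample size; Study Plan and Methods). The earlier study had 54 patients enrolled, 4 CT failures, 50 patients and 52 specimens analyzed, and a CT-pathology correlation of r = 0.7679 (Clinical study, Results). The assumption is that the failure rate of the mixed segmentectomy and wedge series applies to wedge resections alone; the protocol gives no wedge-only rate.

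**The plan's own figures.** 4/54 = 7.41% and 50/54 = 92.6% both reproduce. The 80 cannot be reproduced, because the protocol gives no derivation for it.

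**Expected number with a CT margin.**
- Patients: 80 x 50/54 = 74.1, so about 6 without one.
- The exact (Clopper-Pearson) 95% interval for 4/54 is 2.06% to 17.89%. Then 80 x (1 - 0.0206) = 78.4 and 80 x (1 - 0.1789) = 65.7, a range of about 66 to 78.
- Specimens: 80 x 52/54 = 77.0.
- At a failure rate of 7.41%, the chance that all 80 scans succeed is (50/54)^80, about 0.2%.
- To expect 80 usable CT margins, enrolment would be 80/(50/54) = 86.4, rounded up to 87.

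**Effect on the correlation.** The Fisher-z interval is tanh(atanh(0.7679) ± 1.96/√(n - 3)).

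| n | 95% CI for r | Width | Relative to n = 80 |
|---|---|---|---|
| 80 | 0.659 to 0.845 | 0.186 | 1 |
| 74 | 0.654 to 0.848 | 0.193 | 4% wider |
| 66 | 0.646 to 0.852 | 0.206 | 11% wider |

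**Effect on the limits of agreement, only if the actual margin is the CT margin.** The half-width of the 95% interval for a limit is 1.96 x SD x √(1/n + 1.96²/(2(n - 1))). This gives 0.376 SD at n = 80, 0.391 SD at 74 and 0.414 SD at 66.

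**Which analyses lose patients.**
- The CT-pathology correlation and the ROC curve need a CT margin and lose the failures.
- The mixed model and Bland-Altman analysis use an actual margin that the Statistics section does not tie to CT. The preclinical section treats pathology as the reference standard, and every specimen goes to routine pathology. These analyses lose patients only if the CT margin is meant.
- Additional resection, questionnaires, pathological margin and complications are on the data list for all patients (Data Collection and Monitoring). A failed scan can be counted as a case in which feedback was not available.

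**What a case is.** The 92.6% in the earlier Results has all 54 enrolled patients as its denominator, including the 4 failures. There, a case is an enrolled patient whether or not the scan worked. The Sample size paragraph itself ends on enrolment. On that reading the figures of 80 agree with each other.

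**The case for a change.** The best argument for a correction is that the Sample size section links its evaluation to the surgical margin, that the failure rate stands just above it, and that the feasibility study kept enrolled and analyzed numbers apart while the new plan does not. The specimen handling is the same, and the protocol describes no step to reduce poor inflation. It offers no reason to expect zero failures, and one added sentence would cost nothing.

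Most of those facts stand. The number of usable CT margins is not stated, and 80 is very probably too high for the correlation and ROC analyses. What does not follow is that a stated figure is wrong. That requires evaluating a case to mean obtaining a usable CT margin, which the text does not say. The number available to each analysis, and the handling of unusable scans, are commonly left to a statistical analysis plan, which is not shown here. Nor does the text show that 80 usable scans was ever the aim. If it was, the matching step would be to enrol about 87 or replace failures, whereas a forecast beside an unchanged 80 would leave the trial exactly as it is.

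**Conclusion.** No change is needed. The protocol leaves a detail unstated, but it does not promise a number that it cannot deliver. On the assumption that 4 failures in 54 carry over to wedge resections, about 74 of 80 patients (66 to 78) would enter the CT-pathology correlation and the ROC analysis, and the decision, questionnaire and pathology outcomes can still draw on all 80. If the actual margin in the mixed model and Bland-Altman analysis is taken from CT, those analyses lose the same few patients.

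The cost is a confidence interval for r about 4% wider, or 11% wider at the unfavourable end of the range. No stated power or precision is missed, because none is stated. An analyst will report the number of usable scans beside each CT-based result, as the feasibility study did, and the reader will then have the right denominator. The forecast of 74 is itself soft, since it rests on four events in a mixed series.

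### Primary outcome (2) and the Sample size section claim an effect of feedback on margins over the course, but with feedback planned in every case a trend cannot be attributed to feedback alone

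*Protocol*

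**What the plan says.** Outcome Measures gives a primary outcome in two parts. The first is the contribution of feedback to the treatment decision and the validity of that contribution. The second is "assessing how intraoperative feedback affects surgical margins over the course". The Sample size section gives the purpose of the 80 cases over two years in similar terms, to "evaluate the impact to the surgical outcome" (surgical margin) over the study, and adds that "we will enroll consecutive patients regardless of who the attending surgeon is".

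Study Plan and Methods describes one group at a single centre. After each wedge resection the specimen is scanned, and "Surgeons will wait and refer to these results, and make a decision if additional resection should be made". Once pathology is available, the surgeon is also sent the CT margin alongside the pathological margin. Within each case, "At each surgery, we ask for questionnaire 2 orally before and after resection to assess the contribution of feedback to margin results".

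Statistics assigns one analysis to the over-course question: a linear mixed model of the difference between expected and actual margin. Study Background notes that the previous study gave surgeons no intraoperative feedback. That study is not named as a comparator in Outcome Measures or Statistics.

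**The concern.** The wording of outcome (2) and of the Sample size sentence is causal: feedback is said to affect, or have an impact on, margins as the study proceeds. To support such a claim, a design needs some contrast in exposure to feedback that is not also a contrast in something else. None is planned here. Every case is to be done with feedback, and a surgeon's accumulated feedback grows as that surgeon's study cases accumulate.

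Two wrong conclusions then fit the primary outcome as worded. A significant trend could be reported as an effect of feedback when part or all of it is background change. A flat trend could be reported as no effect when a real effect was offset, or was already complete after the first few cases. There is a further difficulty with the modelled quantity. It is a gap between an expectation and a result, so it can move because surgeons change what they expect, with no change in the margins they cut.

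**Working it through.** **1. What the plan lets one compare.** The inputs are 80 cases and up to 9 surgeons (Sample size), and feedback planned in each case (Study Plan and Methods).

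- Cases done before a surgeon has received any study feedback: at most one per surgeon, so at most 9/80 = 11.25%.
- Cases done after some feedback: at least 71/80 = 88.75%.
- Sample size expects that not all 9 surgeons will contribute. With 5 surgeons (assumed), the first group is 5/80 = 6.25%.

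These first cases are not designated as a baseline and are too few to serve as one.

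**2. Accumulated feedback against case order.** If every scan succeeds, a surgeon's k-th study case follows k − 1 earlier feedback cases. Within a surgeon, accumulated feedback is then case order minus a constant, and the correlation is 1. General experience, growing familiarity with the study procedure, or anything else that follows a surgeon's case order enters the model through the same term. Failed scans loosen this slightly. In the earlier study 4 of 54 patients (7.4%) had an undetectable tumour, and 0.074 × 80 ≈ 6 cases here if that rate carried over (an assumption, since that cohort mixed segmentectomy and wedge resection). Such failures are not a comparator: they are not allocated, and may depend on the specimen.

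**3. Accumulated feedback against calendar time.** These are not identical, because surgeons differ in volume and timing and both surgery date and surgeon number are recorded (Data Collection and Monitoring). Separation is poor, however. In simulated sequences of 80 cases with 5 or 9 surgeons (volumes assumed), calendar date accounted for at least about 80% of the within-surgeon variation in accumulated feedback. The variance inflation is then at least about 1/(1 − 0.80) = 5. A common calendar drift can therefore be separated from accumulated feedback in principle, but imprecisely.

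**4. How readily background change gives a significant trend.** Illustration with zero effect of feedback:

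- SD 8.52 (CT margin in the earlier study; mm assumed, as no unit is printed).
- n = 80 equally spaced, independent cases, with time scaled from 0 to 1.
- Sum of squares of time = (n² − 1)/(12n) = 6399/960 = 6.666, with square root 2.582.
- For a total drift D over the study, the noncentrality is δ = D × 2.582/8.52, and P(significant) = Φ(δ − 1.96) + Φ(−δ − 1.96).

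| Assumed drift D (mm) | δ | P(p < 0.05) |
|---|---|---|
| 0 | 0 | 5% |
| 2 | 0.61 | 9% |
| 4 | 1.21 | 23% |
| 6 | 1.82 | 44% |
| 8 | 2.42 | 68% |

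A simulated mixed model with random surgeon intercepts (9 surgeons, intraclass correlation 0.1 assumed, 300 runs per setting) gave 4.7%, 23.7% and 68.3% for drifts of 0, 4 and 8 mm. Random intercepts do not remove the confounding. The drift sizes are assumptions, and the SD is for raw margin, not for the expected-minus-actual difference, so the table shows the mechanism and does not predict a rate for this trial.

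**5. The plan's own figure.** The 80 cases come with no effect size, SD or power, so there is no calculation to reproduce.

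**The case against.** The strongest reply is that the protocol does contain a contrast. In every case the first wedge is cut and measured before the surgeon sees that result, and questionnaire 2 is taken before and after resection. That is correct, and it supports a statement about what feedback contributed within a case, through the decision on additional resection. One may even read part of outcome (2) that way. It does not support the words about the course of the study, which concern change from case to case.

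A second reply is that the Statistics sentence is already descriptive and that nothing says a trend will be reported as causal. The first half is fair. The outcome that the analysis serves, however, is worded as an effect, and results are reported against the outcome. Nor can the matter be left to a statistical analysis plan, because the single-group design and the primary outcome are fixed in the protocol and no model can supply the missing contrast.

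Some stronger readings are tempting and are not supported:

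- **That the effect is not estimable at any sample size.** This holds for a yes/no exposure indicator, which is planned to be constant. Accumulated feedback per surgeon does vary and is not fully collinear with calendar date.
- **That all 80 cases will in fact receive usable feedback.** This is the plan; the earlier failure rate suggests that a few will not.
- **That Aim 1 has the same fault.** Its text, "Aim1: To assess how surgical outcomes are impacted by intraoperative CT feedback", mentions neither margins nor the course of the study, and the within-case decision can satisfy it.
- **That the earlier CT–pathology difference (11.74 − 10.08 = 1.66) measures how far expectations would shift.** The protocol does not say on which scale surgeons form expectations, or which margin counts as actual in the mixed model.

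**Conclusion.** The point holds for outcome (2) and the Sample size sentence. Both claim an effect of feedback on margins over the course, and the design can only describe a trend among cases done with feedback. Within a surgeon, accumulated feedback and study case order are the same term apart from failed scans. Calendar drift, case mix and surgeon mix can be separated only in part and imprecisely. The modelled gap can also move through expectations alone. At least 71 of 80 planned cases (88.8%) follow earlier feedback to the same surgeon. How much background change will occur is unknown; the 23% and 68% figures rest on assumed drifts of 4 and 8 mm and a borrowed SD. The conclusion itself needs none of those assumptions, only that feedback is planned in every case and that no comparator is named. The trial remains useful, and the within-case part of the primary outcome is untouched. This should be corrected because it concerns one of the two parts of the primary outcome.

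**What to change.** Three wording changes in the Protocol:

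1. **Outcome Measures, outcome (2):** describe the change in surgical margin, and in the difference between expected and actual margin, over successive cases performed with feedback.
2. **Sample size:** replace the impact wording with a descriptive purpose, for example to describe surgical margin over the course of the study.
3. **Statistics:** add one sentence stating that, because feedback is planned in all cases, a trend cannot be attributed to feedback alone and the absence of a trend does not show the absence of an effect.

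Reporting surgical margin itself alongside the expected–actual difference, as item 1 does, also shows whether a change in the gap came with a change in the margins cut. Aim 1 and the wording on the within-case contribution of feedback stay as they are.

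The cost is wording only: no new patients, visits or data. The downside is a less ambitious primary claim for the over-course part.
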